#### 5.3 Screening and Enrollment Procedures

- 5.3.1 Subjects seeking orthodontic treatment through the Byte+ network of dentists will be pre-screened for enrollment.
- 5.3.2 Subjects shall meet all inclusion and none of the exclusion criteria. Subject scanned will be invited to participate in the study. If they agree and consent to participate, they will be included and subsequently enrolled in this study.
- 5.3.3 Subjects will be enrolled on a convenience basis by their voluntary selection to participate in a clinical study after first expressing interest in aligner therapy.
  - Consented subjects will be assigned a unique subject identification number randomly generated by the ERP system. This number will be used as the primary identifier on all study related documents. In addition subject will receive a subject Id when enrolled in the study. Subject IDs are unique to each individual subject and cannot be changed.

All screening activities shall be documented in the screening Log, including but not limited to the determination of eligibility for each screened subject Any protected health information shall be deidentified. The Sponsor shall be able to review protected health information upon request for the purpose of study data monitoring.

#### 5.4 Subject Consent/Assent Procedure

- 5.4.1 Subjects will be fully informed of the nature of the study, the risks involved in participating in the study, and the procedures that will need to be followed during the study period.
- 5.4.2 The Investigator shall explain the terms of the clinical study, objectives of the research being conducted, benefits and risks of participation, benefits and risks of not participating, duration of the study, possible continuation of treatment after the study ends, subject responsibilities, subject compliance, and subject expectations.

**CONFIDENTIAL:** The information in this study protocol is strictly confidential and is available for review to Investigators, study center personnel, the ethics committee, and the health authorities. It will not be disclosed to third parties without written authorization from the Sponsor, except to obtain informed consent from persons receiving the study treatment. Once the protocol is signed, its terms are binding for all parties.

- 5.4.3 It is important that the Investigator discusses alternative and traditional (non-research) treatments available, as well as the risks and benefits of those options.
- 5.4.4 All subjects are required to go through the formal consent process and sign and date the consent form prior to participating as a study subject in this study.
- 5.4.5 Informed Consent is required prior to participation in this study. Eligible subjects, 18 years of age or older, who are willing to participate in the study will read and sign the written, study specific Informed Consent Form prior to undergoing any study-specific procedures.
- 5.4.6 Assent: Eligible subjects under the age of 18 require parental consent to participate in this study, in addition to the subject's consent for participation. Eligible subjects under the age of 18 will require a parent or legal guardian's approval via the study specific Informed Consent Form prior to undergoing any study-specific procedures.
- 5.4.7 Each subject will receive a copy of their signed Informed Consent Form.
- 5.4.8 The study Informed Consent Form does not replace any consent-fortreatment agreement the Investigator currently requires to accept and begin treatment.
  - The enrolled subject (or parent/legal guardian's if applicable) will be offered a rebate for their participation in this study. The subject will receive a rebate on their aligner order following enrollment in the study, and an additional rebate upon compliant and successful completion of aligner therapy under this study protocol. Providing discounts or payments to clinical study subjects in exchange for their participation is a common and, in general, acceptable practice. These actions are not considered a benefit that would be part of the weighing of benefits or risks; it is a recruitment incentive.
  - If the subject is removed from the study by the Sponsor or Investigator due to non-compliance to the study protocol, they will not be eligible for the second rebate, attained at the end of the study.

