# 6.2 Accountability of Investigational Product (IP)

All investigational and control devices must be accounted for.

- 6.2.1 Accountability of all investigational and control devices provided to the Investigator shall be documented by the Sponsor and the Investigator.
- 6.2.2 Accountability of all investigational and control devices provided to the subject shall be documented by the Investigator.

- 6.2.3 The documentation shall provide lot/batch/serial numbers and any pertinent tracking or traceability information provided on product labels or packaging.
- 6.2.4 This information shall be maintained in the clinical trial master file for the life of investigational device.
- 6.2.5 Used investigational and control devices will not be returned to the Sponsor.
- 6.2.6 Any unused investigational and control devices provided to subjects shall be returned to the Sponsor at the end of the study, at the expense of the Sponsor.

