# 7. RISKS AND BENEFITS OF PARTICIPATION

#### 7.1 **Risks**

- 7.1.1 The Sponsor has not identified any additional risks by participation in this clinical study. However, there are some risks that have an increased probability of occurrence with a reduced wear time aligner regimen including:
  - Reduced wear time causes teeth to shift while aligner is not worn; treatment takes longer than expected → Treatment Delay
  - Only wearing aligners for 10-12 hours per day can lead to greater subject discomfort when aligners are worn → Subject Discomfort
- 7.1.2 Additionally, there are risks associated with orthodontic treatment in general, including:
  - Discomfort: There may be some discomfort due to wearing an aligner for the first time, as the mouth is very sensitive. As the teeth move, often some discomfort is to be expected, however this usually wears off in a couple of days after each aligner tray

change. Aligners may cause irritation to the surrounding cheeks and lips.

- Allergy: Although rare, some people may be allergic to the plastic in aligners. If the subject knows that they have a plastic allergy or sensitivity, they should notify the Investigator prior to starting aligner therapy. Subject with known allergies to plastic materials are not eligible to participate in this clinical study. If an allergy to the aligner occurs, the Sponsor and/or the Investigator may recommend that treatment be paused and continued using alternative methods.
- Cavities: The surface of teeth may become weaker, and may have more cavities. Excellent oral hygiene will help to prevent this from happening during treatment.
- Resorption: The roots of teeth may become shorter or weaker during treatment. The Sponsor and/or the Investigator may recommend that treatment be paused if this process called root resorption occurs.
- Tooth movement not tracking according to the prescribed treatment plan: This can be caused by several factors; the top factor being subject compliance in wearing aligners the required number of hours per day/night. Treatment time may take longer than expected, or final outcomes may be different than what was planned when aligners are not worn as prescribed.
- X-ray: Standard procedures will be used i.e., all attempts to limit X-ray exposure will be made during the clinical study, including proper shielding.

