## 8.8 In-Treatment Period

- 8.8.1 The subject will check in with the Investigator at their dental practice/office monthly (every 4-6 weeks).
  - The Investigator will review the subject's treatment progress and provide feedback to the subject and the Sponsor related to compliance and tracking via completion of a visit worksheet at each visit (T1, T2, T3, etc.).
  - The Investigator will also take subject progress intraoral and extraoral photographs at each check in visit and submit them to the Sponsor.
  - In-treatment subject questionnaire
- 8.8.2 The Investigators and the Sponsor will assess the progression of investigational treatment through information subject submitted to the **eCRF**.

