#### 16.4 Subject Withdrawal

- 16.4.1 During the informed consent process, eligible study subjects will be advised that they are free to withdraw their consent to participate in the study at any time, without prejudice by the Sponsor.
- 16.4.2 Every reasonable effort should be made to ensure that each subject complies with the protocol and completes all study visits. However, a subject may withdraw or be withdrawn from participation if:
  - The subject withdraws consent,
  - CoCR or study Investigators recommend discontinuation in the interest of the subject's safety (i.e., AE-related) or because of significant and irremediable protocol non-compliance,
  - There is a report of a SAE that warrants discontinuation,
  - The subject is lost to follow-up, or
  - The Sponsor or the Institutional Review Board (IRB) terminates the clinical trial.
- 16.4.3 Data for subjects that are withdrawn from the study, but have already completed a portion of the trial, will be retained and used in the statistical analyses described in this protocol.
- 16.4.4 Withdrawals from the study shall be documented, with the primary reason for withdrawal recorded by the Investigator.

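### The second rebate requires compliant and successful completion, with success undefined, so subjects who stop early or are judged unsuccessful have no payment tied to the final scan

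*Combined protocol and SAP*

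**What the plan says.** Section 5.4.8 describes two payments. The first carries no condition beyond joining: "The subject will receive a rebate on their aligner order following enrollment in the study". The second is "an additional rebate upon compliant and successful completion of aligner therapy under this study protocol". For a subject removed by the sponsor or investigator for non-compliance, the next bullet says "they will not be eligible for the second rebate, attained at the end of the study". The section describes the payments as a whole thus: "it is a recruitment incentive".

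Other sections that bear on this:

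- **Completion (8.9.3).** Participation ends through completion when the device course is finished and the investigator decides that a retainer can be ordered. Section 12.2.1 says that investigators are not blinded.
- **Final scan (8.3, 8.9.1).** The post-treatment intraoral scan belongs to the final visit.
- **Discontinuation (8.10.3).** Subjects are asked for reasons and safety issues and are seen if possible. No scan is listed.
- **Withdrawal (16.4).** Subjects are told that "they are free to withdraw their consent to participate in the study at any time, without prejudice by the Sponsor". Data already collected are kept and used.
- **Wear.** Section 7.1.2, on teeth not tracking to plan, describes "the top factor being subject compliance in wearing aligners the required number of hours per day/night". Under 8.8.1 the investigator gives feedback "related to compliance and tracking via completion of a visit worksheet at each visit". Section 6.2.5 states: "Used investigational and control devices will not be returned to the Sponsor".
- **Evaluable subjects (4.2).** Compliance is part of the description of the 23 subjects required per arm.

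**The concern.** A payment at the end of a trial normally serves to secure the final data. This one is tied to how treatment went. Its conditions exclude, or may be read to exclude, the subjects whose final scans are most likely to be missing: those who stop, those with adverse events and those whose teeth did not move as planned. If poor results go missing more often in one arm than in the other, a comparison among completers is distorted, and nothing in the stored data would show by how much.

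There is also a reporting problem. Section 16.4.2 allows discontinuation for safety or for non-compliance. A subject who reports a problem, or admits to low wear, may therefore be starting a process that ends in loss of the rebate. Adverse events are the primary safety endpoint, and compliance helps to decide who is evaluable.

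**Working it through.** **The plan's own figure.** The plan gives no number for the rebate or its effect. The nearest figure is the 23 per arm, because compliance is part of its description. With difference 1, SD 1, two-sided alpha 0.05 and power 0.90 (12.1.2), the normal approximation is n = 2 × (1.960 + 1.282)² × 1²/1² = 21.0, rounded up to 22. The exact two-sample t-test needs 22.02, rounded up to 23, with power 0.912 at 23. The stated figure is reproduced, and the rebate wording does not change it.

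**Step 1: who meets the condition.** *Successful* is not defined in 5.4.8, and section 9.3 sets no PAR threshold that payment could refer to. Two readings are open: finishing the course, or finishing with a good result. The retainer judgement in 8.9.3 gives the second some support.

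| Subject (rows 1 and 2 assumed compliant) | Read as finishing the course | Read as a good result |
|---|---|---|
| Finishes, good result | paid | paid |
| Finishes, judged unsuccessful | paid | not paid |
| Stops early for an adverse event | not paid | not paid |
| Withdraws consent | not paid | not paid |
| Removed for non-compliance | not paid (stated) | not paid (stated) |

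Only row 2 depends on the reading. Rows 3 and 4 follow from the requirement to complete therapy.

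**Step 2: which data need the final visit.** From 9.3.1, with TS the pre-treatment, TP the planned and TF the post-treatment PAR score:

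- PIM = (TS − TP)/TS × 100
- AIM = (TS − TF)/TS × 100
- Accuracy is calculated from PIM and AIM.

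PIM needs no final scan. AIM and accuracy both need TF. The schedule in 8.3 places the post-treatment scan at the final visit only. The refinement scan at follow-up visits is taken only if the investigator thinks it necessary, and it is not the TF scan. Section 8.10.3 asks for no scan at discontinuation. Keeping withdrawn subjects' data under 16.4.3 therefore supplies neither AIM nor accuracy for someone who left without a scan.

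**Step 3: room for loss.** The plan enrolls up to 50 per arm and requires 23. So 50 − 23 = 27 subjects, or 27/50 = 54% of an arm, may be lost with the target still met. The target would give no warning of selective loss.

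**Step 4: the compliance condition.** No wear sensor, indicator or diary is described. Compliance reaches the record through the investigator's worksheet every 4–6 weeks, and used aligners do not go back to the sponsor. Hours worn at home can then hardly be known except from the subject, although the protocol never says that wear is self-reported. Over-reporting could move a subject into the compliant group. It cannot alter a PAR score taken from scans by an external evaluator (12.2.7).

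**Step 5: size.** The rebate amount is not stated. Neither the pull on attendance nor the pull on reporting can be estimated.

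**The case against.** A completion bonus that rewards adherence also encourages actual wear, which the protocol treats as the main determinant of tracking. Dropping every compliance condition could lower true wear, perhaps most in the 20–22 h arm. This stands, and it is why the compliance condition is treated below as a choice and not as an error.

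Existing provisions also soften the loss of data. Section 8.10.3 requires discontinuing subjects to be asked about safety and their safety events to be followed. Poor trackers may be offered a refinement, and retainers follow completion. The first rebate is not at risk, and missing a bonus is not a stated penalty for withdrawal, so the conflict with 16.4.1 is one of spirit at most. The consent form is not among the documents reviewed, so it may contain terms for adverse-event withdrawals. All this stands, but none of it secures a final scan.

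Three stronger inferences are tempting and are not supported:

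- **Payment depends on the study outcome.** This is one reading of an undefined word. The only expressly stated ground for forfeiture is removal for non-compliance.
- **Subjects report their own hours and are paid to inflate them.** Self-report is inferred, and the questionnaire items shown in 9.2 and 9.4 include no wear question.
- **Hidden under-wear in the control arm pulls the result towards no difference.** The prescribed contrast is 20 − 12 = 8 to 22 − 10 = 12 h/day. If controls alone wore 60–80% of prescription (an assumption), it would be 0.6 × 20 − 12 = 0 to 0.8 × 22 − 10 = 7.6 h. The same shortfall in both arms gives 0.6 × (20 − 12) = 4.8 to 0.8 × (22 − 10) = 9.6 h. Neither range depends on the rebate, and the documents do not show that the rebate causes under-wear.

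**Conclusion.** The point holds as a weakness in the payment wording. The second rebate rests on an undefined success condition and, as written, excludes anyone who stops early. It therefore gives no payment for the post-treatment scan to the subjects least likely to provide one, and gives subjects with problems a money reason to keep quiet or stay on. Over-reported wear is a secondary risk that acts through compliance classification, not through PAR.

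The size is unknown: the rebate amount is missing, and the documents do not settle the direction of any bias in the efficacy comparison. The conclusion assumes that 5.4.8 is applied as worded and that the consent form does not already provide otherwise. It is an inexpensive improvement worth making, not evidence that the comparison is biased.

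**What to change.** In 5.4.8, delete the success condition and pay the second rebate for attending the final or early-termination visit and providing the intraoral scan and questionnaires, whatever the treatment result or any adverse event. Say the same in the consent form. Add the scan and questionnaires to 8.10.3 so that an early-termination visit has defined content.

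Whether to keep a compliance condition is for the sponsor and IRB, weighing honest reporting against actual wear. If it is kept, tell subjects that reporting low wear hours does not by itself forfeit payment. Check that assurance against 10.1.3, which makes any unapproved deviation end eligibility to continue, whereas 8.10.1 refers to severe non-compliance. The two passages must be reconciled before the assurance can be given.

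The cost is a few more rebates, and a protocol and consent wording change that needs IRB approval.

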# 6. INVESTIGATIONAL DEVICE

# 6.1 **Device Description**

- 6.1.1 All investigational and control aligner devices will be made using FDA cleared plastic materials [Essix ACE (PETG), K062828].
- 6.1.2 Nighttime Aligners are indicated for the treatment of tooth malocclusion in subjects with permanent dentition (i.e., second molars). The aligner system positions teeth by way of continuous gentle force. These aligners

are to be worn by the subjects continuously for 10-12 hours per day (or night); aligners may be removed for small periods of time while eating, drinking or brushing. Subjects will wear each aligner tray for 1-2 weeks, or as instructed by their dentist. When worn while sleeping, the therapy complements the circadian rhythm of bone remodeling and metabolism for tooth movement. Smaller incremental tooth movements are programmed into each aligner tray/stage allowing for activation of biological cascade governing orthodontic tooth movement, with an added advantage of intermittent force resulting in reduced root resorption. Nighttime aligners (investigational) are made with material that is 0.35-0.40 inch thick and the planned tooth movement rate is 20% less than that of the Daytime Aligners (control).

# Tooth movement treatment planning constraints of Nighttime Aligners (investigational):

Movement Type	Translate [B/L] (mm)	Torque / Incline (°)	Tip (°)	Rotate (°)	Intrude (mm)	Extrude (mm)
Per aligner	0.25 mm	1 °	1 °	1.6 °	0.1 mm	N/A
Tooth	Totals per treatment plan					
Incisors	5	25	25	45	2.5	N/A
Laterals	5	25	25	45	2.5	N/A
Canines	3	25	25	35	2.5	N/A
Premolars	2	10	10	10	1	N/A
Molars*	N/A	N/A	N/A	N/A	N/A	N/A

\*Movements of molar teeth are not in the treatment plans for these aligners.

6.1.3 Daytime Aligners are indicated for the treatment of tooth malocclusion in subjects with permanent dentition (i.e., second molars). The aligner system positions teeth by way of continuous gentle force. These aligners are to be worn by the subject 20-22 hours per day and night; aligners may be removed for small periods of time while eating, drinking or brushing.

Subjects will wear each aligner tray for 1-2 weeks, or as instructed by their dentist. When worn while sleeping, the therapy complements the circadian rhythm of bone remodeling and metabolism for tooth movement. Smaller incremental tooth movements are programmed into each aligner tray/stage allowing for activation of biological cascade governing orthodontic tooth movement, with an added advantage of intermittent force resulting in reduced root resorption. Daytime aligners (control) are made with material that is 0.30-0.35 inch thick and the planned tooth movement rate is 20% more than that of the Nighttime Aligners (investigational).

Tooth	movement	treatment	planning	constraints	of	Daytime	Aligners
(contro	ol):						

Movement Type	Translate [B/L] (mm)	Torque / Incline (°)	Tip (°)	Rotate (°)	Intrude (mm)	Extrude* (mm)
Per aligner	0.3 mm	1 °	1 °	2 °	0.1 mm	N/A
Tooth	Totals per treatment plan					
Incisors	5	25	25	45	2.5	N/A
Laterals	5	25	25	45	2.5	N/A
Canines	3	25	25	35	2.5	N/A
Premolars	2	10	10	10	1	N/A
Molars*	N/A	N/A	N/A	N/A	N/A	N/A

\*Extrusive and molar movements are allowable with standard, Daytime Aligners, however, for the purposes of this study, they will not be allowed.

# 6.2 Accountability of Investigational Product (IP)

All investigational and control devices must be accounted for.

- 6.2.1 Accountability of all investigational and control devices provided to the Investigator shall be documented by the Sponsor and the Investigator.
- 6.2.2 Accountability of all investigational and control devices provided to the subject shall be documented by the Investigator.

- 6.2.3 The documentation shall provide lot/batch/serial numbers and any pertinent tracking or traceability information provided on product labels or packaging.
- 6.2.4 This information shall be maintained in the clinical trial master file for the life of investigational device.
- 6.2.5 Used investigational and control devices will not be returned to the Sponsor.
- 6.2.6 Any unused investigational and control devices provided to subjects shall be returned to the Sponsor at the end of the study, at the expense of the Sponsor.

#### 6.3 Study Related Materials

- 6.3.1 All investigational materials provided to the Investigator shall be documented by the Sponsor.
- 6.3.2 All investigational materials provided to subject shall be documented by the Investigator.
- 6.3.3 All documents and study related materials required to conduct this study will be provided to each Investigator by the Sponsor. Additional materials may be sent upon request.

# 7. RISKS AND BENEFITS OF PARTICIPATION

#### 7.1 **Risks**

- 7.1.1 The Sponsor has not identified any additional risks by participation in this clinical study. However, there are some risks that have an increased probability of occurrence with a reduced wear time aligner regimen including:
  - Reduced wear time causes teeth to shift while aligner is not worn; treatment takes longer than expected → Treatment Delay
  - Only wearing aligners for 10-12 hours per day can lead to greater subject discomfort when aligners are worn → Subject Discomfort
- 7.1.2 Additionally, there are risks associated with orthodontic treatment in general, including:
  - Discomfort: There may be some discomfort due to wearing an aligner for the first time, as the mouth is very sensitive. As the teeth move, often some discomfort is to be expected, however this usually wears off in a couple of days after each aligner tray

change. Aligners may cause irritation to the surrounding cheeks and lips.

- Allergy: Although rare, some people may be allergic to the plastic in aligners. If the subject knows that they have a plastic allergy or sensitivity, they should notify the Investigator prior to starting aligner therapy. Subject with known allergies to plastic materials are not eligible to participate in this clinical study. If an allergy to the aligner occurs, the Sponsor and/or the Investigator may recommend that treatment be paused and continued using alternative methods.
- Cavities: The surface of teeth may become weaker, and may have more cavities. Excellent oral hygiene will help to prevent this from happening during treatment.
- Resorption: The roots of teeth may become shorter or weaker during treatment. The Sponsor and/or the Investigator may recommend that treatment be paused if this process called root resorption occurs.
- Tooth movement not tracking according to the prescribed treatment plan: This can be caused by several factors; the top factor being subject compliance in wearing aligners the required number of hours per day/night. Treatment time may take longer than expected, or final outcomes may be different than what was planned when aligners are not worn as prescribed.
- X-ray: Standard procedures will be used i.e., all attempts to limit X-ray exposure will be made during the clinical study, including proper shielding.
- 7.1.3 Accidental Disclosure of Personal Health Information: Although rare, there is a risk that personal health information may be disclosed to others who do not have the right to see it. The US HIPAA and EU GDPR privacy rules help your dentist and the Sponsor ensure they have the appropriate processes in place to prevent this from occurring.

[figure not shown]
